 - o from randomization to the first day of achieving sustained (i.e., at least 2 days) resolution of fever for subjects who presented with fever at any point between enrollment and day 2 post randomization

- with temperature <38C or >=38C experienced in total during the first 28 days post randomization
- o from randomization to the first day post randomization of achieving oxygenation of SpO2>=96% in room air when resting for subjects who presented with SpO2>93% and <96% in room air, when resting, at enrollment
- o with oxygenation of SpO2>= 96% or SpO2>93% in room air, when resting, in total during the first 28 days post randomization

3. COVID-19 related deterioration and mortality

- **3a. Deterioration and mortality rates:** Proportion of treatment group, versus placebo group, respectively, who per subject reporting or medical records by day 14, day 28 and by day 60 post randomization had experienced:
 - o an emergency department visit, other than at study enrollment or study visits
 - hospitalization for COVID-19
 - o hospitalization for COVID-19 requiring oxygen
 - hospitalization for COVID-19 requiring ICU
 - o hospitalization for COVID-19 requiring ventilation
 - o COVID-19 related death
 - death
 - hospitalization or death
- **3b.** *Time to and length of deterioration*: Comparison of treatment group versus placebo group, respectively, in the number of days
 - o from randomization until the first day of experiencing hospitalization for COVID-19
 - o of hospitalization for COVID-19 experienced in total by day 14, by day 28 and by day 60 post randomization
 - o of hospitalization for COVID-19 requiring oxygen experienced in total by day 14, by day 28 and by day 60 post randomization
 - of hospitalization for COVID-19 requiring ICU experienced in total by day 14, by day 28 and by day 60 post randomization
 - o of hospitalization for COVID-19 requiring ventilation experienced in total by day 14, by day 28 and by day 60 post randomization

4. WHO 9-Point Ordinal Scale

- 0. Uninfected or "no clinical or virological evidence of infection"
 - a. defined as subject answering "Yes" to "In the past 24 hours, have you returned to your usual health (before your COVID-19 illness)?"
- 1. Not hospitalized, no limitations on activities
 - a. defined as subject answering "Yes" to "In the past 24 hours, have you returned to your usual activities (before your COVID-19 illness)?"
- 2. Not hospitalized, limitation on activities

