 - a. defined as subject answering "No" to "In the past 24 hours, have you returned to your usual activities (before your COVID-19 illness)?"
- 3. Hospitalized, not requiring supplemental oxygen
- 4. Hospitalized, requiring supplemental oxygen
- 5. Hospitalized, on non-invasive ventilation or high flow oxygen devices
- 6. Hospitalized, intubated
- 7. Hospitalized, advanced life support including invasive mechanical ventilation or ECMO
- 8. Death
- **4a)** Ordinal scale rates: proportion of treatment group versus placebo group, respectively who had experienced:
 - o an improvement from scale 2 at randomization to scale 1 or 0 on days 4, 7, 10, 14, 21, 28, 42, 60 post randomization,
 - o an improvement from scale 1 at randomization to scale 0 on days 4, 7, 10, 14, 21, 28, 42, 60 post randomization
 - o a sustainment from scale 1 at randomization to scale 1 on days 4, 7, 10, 14, 21, 28, 42, 60 post randomization
 - o any improvement of the scale (i.e., at least a 1-point decrease) between enrollment and days 7, 14, 28, 42, 60 post randomization
 - any worsening of the scale (i.e., at least a 1-point increase) between enrollment and days 7,
 14, 28, 42, 60 post randomization
 - o scale 4 or higher by day 28 or day 60 post randomization
 - o scale 6 or higher by day 28 or day 60 post randomization

- *4b) Ordinal scale averages, highs, and lows:* Comparison of treatment group versus placebo group, respectively, at days 14, 28 and 60 post randomization in the
 - o average of daily scale value on that day
 - o overall average of daily scale value experienced since enrollment
 - o in the worst (i.e., highest) daily scale value experienced since enrollment
 - o in the best (i.e., lowest) daily scale value experienced since enrollment
- **4c)** Time to improvement: Comparison of treatment group versus placebo group, respectively, in the number of days from enrollment until first experiencing a 1-point improvement sustained over at least 2 days by day 14, day 28 and by day 60 post randomization
- *4d) Length of ordinal scale experience:* Comparison of treatment group versus placebo group, respectively, in the total number of days by day 14, day 28 and by day 60 post randomization on which subjects experienced a given scale value (i.e., 3, 4, 5, 6, 7)

5. Surrogate markers of COVID-19-related inflammation and organ involvement

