Heart: troponin; Kidney: creatinine, blood urea nitrogen (BUN), electrolytes (calcium, carbon dioxide, chloride, potassium, sodium, magnesium); Pancreas: glucose, HbA1c, lipase; Liver: ALT, AST, ALP, total bilirubin; Muscle weakness: creatinine kinase; Hematology: red blood cell count, hemoglobin, platelet count, prothrombin time (PT), partial thromboplastin time (PTT), ddimer; Immunology: white blood cell count, neutrophils, lymphocytes, monocytes, eosinophils, T cells, SARS-CoV-2 viral load in nasopharyngeal sample, SARS-CoV-2 serology in blood; Inflammation: CRP, ferritin, LDH, caspase-1, IL-18, IL-1β, IL-1 receptor antagonist, gasdermin D, IL-6, TNF-α, G-CSF

- *5a) Analysis and comparison of* surrogate markers of COVID-19 related inflammation and organ involvement as determined by biochemistry, hematology, and immunology labs and studies, in treatment group versus placebo group, respectively, for
 - o values on days 1 (enrollment), 7, 14, 21, 28 post randomization
 - o changes from enrollment to days 7, 14, 21, or 28 post randomization
 - o changes between days 7, 14, 21, 28 post randomization
- *5b) Reference range rates:* proportion of treatment group versus placebo group, respectively, who experience normal / in-range values for a given marker at days 7, 14, 21, 28 post randomization

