8.2 Analysis Methods

General Methods

FDA Data Standard Guidelines will be followed. Continuous variables will be summarized using the number of observations, number of observations above the limit of quantification (if applicable), mean, standard deviation (SD) median, and range. Categorical variables will be summarized using frequency counts and percentages. Comparison of belnacasan (VX-765/RVT-201/MSR-001) and placebo groups will utilize Poisson regression for counts, Cox proportional hazards regression for time-to-event data and mixed effects models for continuous and categorical data obtained over study days.

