8.5 Treatment Effect Analyses

Secondary Endpoint Analyses

Event counts over 60 days will be analyzed by Poisson regression as described above in 8.4. Time

to events will be analyzed by Cox regression. Differences between belnacasan and placebo with

respect to change in continuous endpoints will be assessed by mixed effects models for continuous

repeated measures data and mixed effects logistic models for repeated categorical variables.

Endpoint proportions of belnacasan and placebo groups will be assessed by contingency table

analysis (chi-square).

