8.7 Sample Size Considerations

A total of 40 subjects will be randomized, 20 to belnacasan (VX-765/RVT-201/MSR-001) 900 mg TID and 20 to placebo. As this is a proof-of-concept study, it will likely not be powered to detect belnacasan – placebo differences that are clinically meaningful. For example, the observed difference in endpoint rate ratios would need to be over 60% to achieve 80% power with an alpha error rate of 5% for 20 subjects in each group. This study will provide an estimate of the belnacasan effect size to inform a larger trial where a more clinically meaningful difference can be detected.

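### Section 8.5 compares arms on change but specifies no baseline term, which as directly read costs precision on the laboratory markers that have an enrollment value

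*Combined protocol and SAP*

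**What the plan says.** Section 8.5 holds the only model statement for continuous secondary endpoints: arm differences with "respect to change in continuous endpoints will be assessed by mixed effects models for continuous" repeated-measures data. Section 8.2 gives the same model class in general terms: "mixed effects models for continuous and categorical data obtained over study days". Neither section lists fixed effects, covariates, a covariance structure or an analysis scale, or says how the enrollment value enters the model.

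For the laboratory markers, endpoint 5a in Section 3.4 has three forms: "values on days 1 (enrollment), 7, 14, 21, 28 post randomization"; "changes from enrollment to days 7, 14, 21, or 28 post randomization"; and "changes between days 7, 14, 21, 28 post randomization". Table 1 in Section 5.2 schedules standard labs, immunology tests and the nasopharyngeal sample at the screening/enrollment visit. Section 6.1 gives the first dose only after screening is complete. Most markers therefore have a pre-dose value. As the table reads in the extracted text, blood SARS-CoV-2 antibody is marked only at day 28 and early termination.

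Section 8.7 randomizes 40 subjects, "20 to belnacasan (VX-765/RVT-201/MSR-001) 900 mg TID and 20 to placebo".

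**The concern.** A change score subtracts the whole enrollment value, so it fixes the baseline slope at 1. Unless enrollment and follow-up values are almost perfectly correlated, that is too steep and adds the noise of the enrollment measurement to the comparison. A model that estimates the slope avoids this.

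The secondary objective in Section 3.3 is framed in terms of effect size, and Section 8.7 says the estimate is meant to inform a larger trial. With 20 per arm and low power conceded, the width of the interval around that estimate is much of what the trial delivers. Leaving the baseline term unstated also leaves an analytic choice open until the data can be seen.

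**Working it through.** **The plan's own figure.** Section 8.7 says rate ratios would have to differ by over 60% for 80% power. It gives no control rate, so the figure cannot be uniquely reproduced. It concerns rates and has no bearing on the continuous markers.

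**Inputs.** From the documents: 20 per arm, 1:1 allocation and alpha 5% (taken as two-sided). Assumed: equal SD at enrollment and follow-up (set to 1), correlation rho from 0.3 to 0.95, one follow-up visit, complete and normally distributed data. The documents give no SD and no rho.

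**Formulas, per subject, in SD² units.**
- Change score: 1 + 1 − 2·rho = 2(1 − rho).
- Baseline-adjusted: 1 − rho².
- Ratio, change over adjusted: 2(1 − rho)/(1 − rho²) = 2/(1 + rho).

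The ratio is a large-sample result. Estimating the slope from 40 subjects inflates the adjusted variance by roughly 1 + 1/(40 − 4) = 1.028. A simulation of 20,000 trials at 20 per arm (t-test on change against analysis of covariance) checks the net result. In the table, detectable differences are for 80% power, (1.960 + 0.842)·√(variance·2/20), in SD units. Power is for a true difference of 0.8 SD.

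| rho | Formula ratio | Simulated ratio | Detectable, change vs adjusted | Simulated power, change vs adjusted |
|---|---|---|---|---|
| 0.3 | 2/1.3 = 1.54 | 1.50 | 1.05 vs 0.85 | 55% vs 73% |
| 0.5 | 2/1.5 = 1.33 | 1.29 | 0.89 vs 0.77 | 69% vs 80% |
| 0.7 | 2/1.7 = 1.18 | 1.14 | 0.69 vs 0.63 | 89% vs 92% |
| 0.9 | 2/1.9 = 1.05 | 1.03 | 0.40 vs 0.39 | both about 100% |
| 0.95 | 2/1.95 = 1.03 | 1.00 | 0.28 vs 0.28 | both about 100% |

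Both estimators were unbiased at every rho.

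**95% half-width at rho 0.5.** Change score: 1.96·√(2·1.00/20) = 0.62 SD. Adjusted: 1.96·√(2·0.75/20) = 0.54 SD.

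**Chance imbalance.** The between-arm difference in enrollment means has SD √(2/20) = 0.32. A change score already subtracts baseline, so what remains of an imbalance is a fraction (1 − rho), with the opposite sign. At rho 0.5 a one-SD imbalance shifts the estimate by 0.5 × 0.32 = 0.16 SD. Baseline adjustment removes this shift on average.

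**The other reading of the wording.** The enrollment value could be one of the repeated responses, with the arm effect taken as a group-by-time contrast. If each arm has its own free enrollment mean and data are complete, this gives the same estimate as the change score. If the enrollment mean is constrained equal across arms, it recovers essentially the precision of baseline adjustment. The plan states no such constraint.

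**The case against.** The strongest reply is that the plan is silent, and silence is not a decision. That stands: a reader might infer that the authors chose not to adjust, but no sentence says so, and a mixed model with a constrained enrollment mean fits the same wording. It does not remove the point. Section 8.4 names the exposure-time term and the fallback distribution for the Poisson model, so the authors do name terms where they have settled them. Nothing comparable appears for the mixed models, and the direct reading remains change by arm.

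Scope is the second reply, and it also stands. A reader might extend the point to every continuous secondary endpoint. Several are not changes from baseline: days "of hospitalization for COVID-19 experienced in total by day 14, by day 28 and by day 60 post randomization", which have no baseline value at all; day counts of temperature or SpO2; the "overall average of daily scale value experienced since enrollment" and the worst and best values; and, within 5a, changes between post-baseline days. Serology appears to lack an enrollment sample.

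A reader might also infer that markers will be analyzed on the raw scale. No analysis scale is stated, so that too rests on silence and is a separate matter.

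Finally, the trial calls itself hypothesis-generating and probably underpowered, and no secondary endpoint drives a decision rule. This limits the importance. It does not make the adjustment less worthwhile, because the effect-size estimate is the declared product.

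**Conclusion.** The point holds for endpoint 5a markers that have an enrollment value. As directly read, Section 8.5 is an unadjusted change-score comparison. Its variance at 20 per arm is about 50%, 29% or 14% above that of a baseline-adjusted analysis at assumed correlations of 0.3, 0.5 or 0.7, about 3% at 0.9 and nil near 0.95. These sizes rest on equal SDs at enrollment and follow-up and on correlations that the documents do not supply.

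A reader might go further and infer biased effect estimates, or that a chance imbalance passes in full into the result. Neither follows: randomization leaves both estimators unbiased, and only the fraction (1 − rho) carries over. The primary safety analysis, a Poisson comparison of adverse events, is not affected. The change is worth making because it is nearly free.

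**What to change.** Add to Section 8.5: *For endpoint 5a markers with an enrollment value, post-baseline values at the visits where the marker is scheduled will be modelled with arm, visit, arm-by-visit and the enrollment value as fixed effects.* An acceptable alternative is to keep enrollment as a response with its mean constrained equal across arms.

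The enrollment value costs one parameter per model. A baseline-by-visit term may be added; with four post-baseline visits (days 7, 14, 21, 28) it costs three more, and fewer for markers scheduled less often. In a 40-subject trial that is a choice to make deliberately. No new data or visits are needed.

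Leave out the endpoints listed above that are not changes from baseline, and serology unless an enrollment sample is confirmed. Stating whether skewed markers will be log-transformed is a separate, optional clarification.

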Statistical **Study Populations: Considerations** • Safety & Tolerability Population: All enrolled subjects who have received at least 1 dose of IP (belnacasan or placebo) will be studied. Even if subjects have discontinued study treatment, as long as they maintain consent, they will continue to be in the study and included in analysis, i.e., their safety and tolerability information will continue to be collected for at least 60 days. • Treatment Effect Evaluable Populations: All enrolled subjects who have received at least 1 dose of IP (belnacasan or placebo) will be studied. Even if subjects have discontinued study treatment, as long as they maintain consent, they will continue to be in the study and included in analysis, i.e., their outcome information will continue to be collected for at least 60 days. **Analysis Methods:** FDA Data Standard Guidelines will be followed. Continuous variables will be summarized using the number of observations, number of observations above the limit of quantification (if applicable), mean, standard deviation (SD) median, and range. Categorical variables will be summarized using frequency counts and percentages. Comparison of belnacasan and placebo groups will utilize Poisson regression for counts, Cox proportional hazards regression for time-to-event data and mixed effects models for continuous and categorical data obtained over study days. **Primary Safety and Tolerability Analysis:** All safety & tolerability analyses will be performed on the Safety Population. The safety data will be presented in individual listings and summary tables. Overall safety will be assessed by the number of belnacasan dosed subjects experiencing a grade 4 or 5 SAE during the trial. Of 20 subjects enrolled in the belnacasan group, 3 or more developing grade 4 or 5 SAE probably related to belnacasan would be considered unlikely due to chance. Therefore, belnacasan will be determined safe if no more than 2 subjects develop a grade 4 or 5 SAE in the belnacasan group probably related to belnacasan. In terms of stopping rules, should two or more subjects develop a similar Grade 3 SAE that is at least possibly related to belnacasan or should one or more subjects develop a \geq Grade 4 SAE that is at least possibly related to belnacasan, the trial will be paused for DSMB safety review. **Secondary Treatment Effect Endpoint Analysis:** Event counts over 60 days will be analyzed by Poisson regression. Time to events will be analyzed by Cox regression. Differences between belnacasan and placebo with respect to change in continuous endpoints will be assessed by mixed effects models for continuous repeated measures data and mixed effects logistic models for repeated categorical variables. Endpoint proportions of belnacasan and placebo groups will be assessed by contingency table analysis (chi-square). **Sample Size Considerations:** As this is a proof-of-concept study, it will likely not be powered to detect belnacasan - placebo differences that are clinically meaningful. For example, the observed difference in endpoint rate ratios would need to be over 60% to achieve 80% power with an alpha error rate of 5% for 20 subjects in each group. This study will provide an estimate of the belnacasan effect size to inform a larger trial where a more clinically meaningful difference can be detected. **Initial Date** November 2021 **Completion Date** April 2022

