3.4 Secondary Endpoints

1. Clinical recovery and resolution of COVID-19 symptoms

1a. Sustained recovery and resolution rates of common COVID-19 symptoms:

(i.e., stuffy or runny nose, sore throat, cough, low energy or tiredness, muscle or body ache, headache, chills or shivering, feeling hot or feverish, nausea, vomiting, diarrhea, shortness of breath with exertion; impairment in sense of smell or taste)

Proportion of subjects in treatment group versus placebo group, respectively, who per symptom questionnaire on days 4, 7, 10, 14, 21, 28, 42, 60 post randomization have achieved for two consecutive days:

- o scores not higher than 0 for all symptoms
- o scores not higher than 1 for all symptoms
- o scores not higher than 0 for all symptoms other than impairment of taste or smell
- o scores not higher than 1 for all symptoms other than impairment of taste or smell
- *1b. Sustained improvement of global impression rates:* Proportion of subjects in treatment group versus placebo group, respectively, who per symptom questionnaire on days 4, 7, 10, 14, 21, 28, 42, 60 post randomization have answered for two consecutive days
 - "Yes" to "In the past 24 hours, have you returned to your usual health (before your COVID-19 illness)?"
 - "Yes" to "In the past 24 hours, have you returned to your usual activities (before your COVID-19 illness)?"
 - o "None" to "In the past 24 hours, what was the severity of your overall COVID-19 related symptoms at their worst?"
 - o "Mild" to "In the past 24 hours, what was the severity of your overall COVID-19 related symptoms at their worst?"
- 1c. Time to sustained recovery, resolution or improvement: comparison in treatment group versus placebo group, respectively of the number of days from randomization to the first day of achieving each item in 1a and 1b above.

2. Physical functions and parameters relevant to COVID-19

- **2a. Parameter rates:** Proportion of subjects in treatment group versus placebo group, respectively, who on days 4, 7, 10, 14, 21, 28, 42, 60 post randomization per thermometer or pulse oximeter reading experienced:
 - fever at any point between enrollment and day 2 post randomization and who were afebrile <38C
 - o oxygenation of SpO2>=96% or >93% in room air when resting
- 2b. Time to and length of parameters: comparison in treatment group versus placebo group, respectively of the number of days

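### Section 8.5 and the Synopsis analyse binary proportions by chi-square with no effect measure or interval, and do not keep the mixed logistic model away from cumulative endpoints

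*Combined protocol and SAP*

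**What the plan says.** The secondary objective (section 3.3) is defined through effect size in five outcome areas, and section 8.7 says: "This study will provide an estimate of the belnacasan effect size to inform a larger trial". The size of the trial is also in 8.7: "A total of 40 subjects will be randomized, 20 to belnacasan", with 20 more on placebo.

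Section 8.5, repeated in the Synopsis, gives two routes for binary endpoints:

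- "Endpoint proportions of belnacasan and placebo groups will be assessed by contingency table" analysis, with chi-square named as the test.
- "mixed effects logistic models for repeated categorical variables". No random effects, time terms or reported contrast are given.

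Neither route comes with a named effect measure or confidence interval. For counts, by contrast, section 8.4 names the incidence rate ratio. Section 8.2 adds counts and percentages for categorical variables.

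The binary endpoints in section 3.4 are of different kinds:

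- Endpoint 3a is cumulative: "by day 14, day 28 and by day 60 post randomization had experienced" the listed events. So are the two items in 4a on reaching scale 4 or 6 or higher by day 28 or day 60.
- Endpoints 2a and 5b and most of 4a are states on named days, which can reverse.
- Endpoints 1a and 1b can be read either way. In 1a the wording is "on days 4, 7, 10, 14, 21, 28, 42, 60 post randomization have achieved for two consecutive days" the required scores.

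**The concern.** A chi-square p-value carries neither the size nor the direction of a difference, and it says nothing about precision. A planner of the next trial needs all three. With 20 per arm and events such as hospitalization or death, expected counts will often be small, so the p-value itself becomes unreliable.

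The second problem is the missing link between endpoints and methods. A cumulative indicator never returns to zero, so each subject's series is a run of zeros followed by a run of ones. If an analyst sent such a series to the mixed logistic model, the reported odds ratio would depend on where the software stopped rather than on the data.

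**Working it through.** **The plan's own figure.** Section 8.7 says that a difference in rate ratios of over 60% would be needed for 80% power. It gives no baseline rate and no sidedness, so the figure cannot be reproduced. Two-sided, a rate ratio of 1.6 needs about 2.9 control events per subject and a ratio of 0.4 about 1.6. Nothing below depends on it.

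**Inputs.** 20 per arm (8.7); looks at days 14, 28 and 60 (3a) or eight days (1a, 1b). The documents give no event rates, so all counts below are assumed.

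**1. What chi-square returns.** Take 2/20 against 5/20.

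- X² = N(ad − bc)² / (product of the margins) = 40 × (2×15 − 18×5)² / (20×20×7×33) = 144,000 / 92,400 = 1.56, p = 0.21.
- Swapping the arms changes only the sign inside the square, so 5/20 against 2/20 gives the same result.
- Smallest expected count: 20 × 7/40 = 3.5. For 0/20 against 2/20 it is 20 × 2/40 = 1.

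**2. What the same table can return.** Risk difference 0.10 − 0.25 = −0.15. The Wilson limits are 0.028 to 0.301 for 2/20 and 0.112 to 0.469 for 5/20. The Newcombe limits follow:

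- Lower: −0.15 − √[(0.100 − 0.028)² + (0.469 − 0.250)²] = −0.38
- Upper: −0.15 + √[(0.301 − 0.100)² + (0.250 − 0.112)²] = 0.09

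Other assumed tables: 14/20 against 8/20 gives 0.30 (−0.01 to 0.54); 0/20 against 2/20 gives −0.10 (−0.30 to 0.08).

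**3. The mixed logistic model on cumulative data.** The model has visit effects, an arm effect and a normal random intercept with standard deviation σ. The likelihood was maximised at fixed values of σ. The example is 3a with three looks: 0.05, 0.10, 0.10 on belnacasan and 0.15, 0.20, 0.25 on placebo.

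| σ | log-likelihood | arm log odds ratio |
|---|---|---|
| 2 | −32.7 | −1.6 |
| 10 | −25.2 | −6.1 |
| 20 | −24.6 | −12.0 |
| 40 | −24.5 | −23.8 |

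The likelihood is still rising at the largest σ tried, and the log odds ratio grows in proportion to σ (ratio about −0.59). The same happened with all events before day 14 (ratio about −0.45) and with eight cumulative looks (about 0.81). The reason is that a finite σ always gives some probability to a return from one to zero, which never occurs in these data. As σ grows, only the ratio to σ is determined, and it tends to a probit coefficient. In the all-by-day-14 example (2/20 against 4/20), that limit is Φ⁻¹(0.10) − Φ⁻¹(0.20) = −1.28 + 0.84 = −0.44, which agrees with the −0.45 found.

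**4. The same model on reversible data.** With eight on-the-day looks the log-likelihood is −170.1 at σ = 1, −169.9 at σ = 2 and −188.7 at σ = 5. It peaks at a σ of about 1 to 2, with a finite odds ratio of about 1.75 to 1.93.

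**The case against.** The strongest reply is that the estimate is not lost. The endpoints are themselves defined as proportions by arm, section 8.2 calls for counts and percentages, and a contingency table displays them. Anyone can subtract. That stands: a reader might infer that the planned methods cannot yield any effect size, and the documents do not support that. Cox regression also gives hazard ratios for the time-to-event items in 1c, 2b, 3b and 4c. What is missing is a prespecified contrast and interval for the binary endpoints.

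The second reply is that the plan never sends cumulative endpoints to the mixed logistic model. This also stands. The 3a items and the two 4a items are worded as proportions, which 8.5 routes to chi-square. Endpoints 1a and 1b can be read as status on the day, especially as 1c separately covers the first day of achievement. The absence of a finite estimate is therefore a risk created by the missing mapping, not a stated plan. The risk is real because 8.2 sends categorical data collected over study days to mixed models, and nothing excludes the cumulative endpoints.

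A reader might also infer that the mixed logistic model should give way to a marginal model throughout. That does not follow. For reversible states it works, and the choice is one of estimand and of missing-data assumptions. Section 8.6 expects missing longitudinal data, and a likelihood-based mixed model needs a weaker assumption there than an unweighted marginal one.

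Finally, these are secondary endpoints in a hypothesis-generating trial whose primary objective is safety. That limits the weight of the point. It does not remove it, since an effect size is the stated secondary aim.

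**Conclusion.** The point holds in two parts. First, for binary proportions the plan specifies a test where it promises an estimate. No effect measure or interval is named, and the test is unreliable for rare events at 20 per arm. This rests on the text alone; the example counts only illustrate it. Second, because endpoints are not mapped to methods, the mixed logistic model could be applied to 3a, to the 4a items on scale 4 or 6 or higher, or to 1a and 1b read as ever achieved. In that case it has no finite odds ratio. This assumes a random intercept with visit effects, since the plan does not specify the model. It comes from the absorbing pattern and appeared in all three cumulative examples. For reversible endpoints the model gives a usable subject-specific odds ratio. The primary safety analysis is not affected.

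**What to change.** In section 8.5 and in the matching Synopsis paragraph:

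- Replace chi-square as the analysis of proportions with the risk difference, belnacasan minus placebo, at each day named in section 3.4. Give a 95% confidence interval suited to 20 per arm (Newcombe or Miettinen-Nurminen; name one).
- State that cumulative endpoints (3a, and the 4a items on scale 4 or 6 or higher) are analysed this way and not by the mixed logistic model. Add Cox regression only where section 3.4 already defines a time-to-event endpoint. In area 3 that is only time to COVID-19 hospitalization; emergency visits, ICU, ventilation, death and the 4a items have none.
- Say whether 1a and 1b mean status on the day or ever achieved. If ever achieved, they follow the cumulative rule, with Cox regression through 1c.
- Keep the mixed logistic model, if wanted, for reversible repeated states.

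The cost is wording only, with no added subjects, visits or data. The visible downside is wide intervals. By the Wald approximation the half-width is 1.96 × √[2p(1 − p)/20], which is 0.31 at p = 0.5 and 0.25 at p = 0.8. The recommended intervals will differ somewhat and need not be symmetric.
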